12.2 Analysis of Primary Objective

Objective response rate in the patients with high PD-L1 expressing cancers after failure of targeted therapy is the primary outcome of interest. To examine this, a Simon's two-stage design (Simon, 1989) will be used. The null hypothesis that the true objective response rate is 10% will be tested against a one-sided alternative. In the first stage, 8 patients will be accrued. If there are zero responses in these eight patients, the study will be stopped. Otherwise, seven additional patients will be accrued for a total of 15. The null hypothesis will be rejected if 4 or more responses are observed in 15 patients. This design yields a type I error rate of 0.054 and power of 90.5% when the true objective response rate is 40%.

12.3 Analysis of Secondary Objectives

Overall survival (OS) will be determined from the date of progression on primary targeted treatment to death. The three cohorts of interest, described above, will have OS estimated using Kaplan-Meier methods and survival rates will be compared using log-rank tests. Next, objective response rates will be estimates in the two PD-L1 expression < 50% arms. Confidence intervals for each of these rates will be estimated. An exploratory comparison will be made among the three groups comparing CR/PR vs SD/PD among the groups using a Fisher's exact test (for the 2x3 table).

Toxicities for each group will be estimated and described using counts and frequencies by grade, location and relatedness.

The incidence of mutations in secondary genes will be determined for patients in the two PD-L1 expression < 50% arms as well. Next, we will examine whether smoking status (defined as Current, Former, Never) is related to the prevalence of any mutations identified (present/absent) using Cochran-Maentel Haenzel tests. These tests will be performed overall and then separately in the three arms defined above

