1.0 Introduction and Background

Lung cancer (LC) is the third most common cancer in both men and women and the leading cause of cancer death.¹ Non-small cell (NSC) lung cancer includes three main subtypes, squamous cell carcinoma (25%), adenocarcinoma (40%), and large cell carcinoma (10%).² Only approximately 15% of lung cancer cases are diagnosed at the local stage.¹

Major oncogenic drivers in non-small cell lung cancer include mutations in EGFR, translocations in Alk, and translocations in ROS-1. National Comprehensive Cancer Network (NCCN) guidelines also have supported the use of medications targeting BRAF, Met, HER-2, and RET. Investigators have reported emergence of mutations in a secondary oncogenic drivers at the time of progression on tyrosine kinase inhibitor therapy for patients whose tumors harbor primary activating mutations in one of the major three (EGFR, Alk, or ROS-1) drivers.

The plan of care for patients whose cancer progresses on treatment with one of the major 3 driver mutations may include sequencing of the primary driver gene for emergence of an additional mutation in that gene. Immunotherapy may also benefit some patients with acquired resistance, but the role of these medications is not well defined. High PD-L1 expression and response to immunotherapy has been reported in patients with oncogenic drivers who smoke cigarettes.

The use of expanded genetic testing in this situation to identify mutations in genes other than the primary driver gene (secondary mutations) is attractive for exploring all available treatment options. The outcomes of patients who undergo testing and have mutations in a secondary gene have not been prospectively studied. Available options include alternative agent targeting the original driver mutation, changing treatment to target the mutation in the secondary gene, combination therapy targeting both, or other treatments such as chemotherapy, immunotherapy, or clinical trials.

The goal of this protocol is to evaluate the efficacy of treatment tailored to the immunogenic and mutation profiles of patients on EGFR, MET, BRAF, V600E, RET, HER2, Alk, or ROS-1 inhibitors at the time of progression. This pilot study will compare the clinical outcomes for treatment of resistance targeting the primary mutations, secondary mutations, or immunotherapy.

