2.2 Secondary Objective(s)

- 2.2.1 To compare the overall survival for patients receiving treatment targeting primary mutations, secondary mutations, or immunotherapy at the time of progression on tyrosine kinase inhibitor therapy

Phase II Pilot Study Evaluating Strategies to Overcome Resistance at the Time of Progression
for Patients with Non-Small Cell Lung Cancers Harboring Major Oncogenic Drivers
Wake Forest Baptist Comprehensive Cancer Center (CCCFWU)
CCCFWU 62716
ClinicalTrials.gov: NCT02949843

- 2.2.2 To assess the incidence of secondary mutations in this population according to smoking status.
- 2.2.3 To evaluate the response rates of patients treated using these different approaches.
- 2.2.4 To correlate outcomes with specific secondary genetic changes.

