3.0 Patient Selection

3.1 Inclusion Criteria

- 3.1.1 Patients must have histologically or cytologically confirmed incurable non-small cell lung cancer that harbors an activating mutation in EGFR, MET, BRAF, V600E, RET, HER2, translocation in Alk, or translocation in ROS-1.
- 3.1.2 Patients must be receiving treatment or planning to start treatment with a tyrosine kinase inhibitor targeting the activated gene.
- 3.1.3 Patients may not be receiving the treatment targeting the activated gene as part of a clinical treatment trial other than the Precision Oncology Trial.
- 3.1.4 ECOG performance status of 0-3.
- 3.1.5 Patients must have normal organ function as defined below:
 - AST(SGOT)/ALT(SGPT) $\leq 2.5 \times$ institutional upper limit of normal
- 3.1.6 These agents may be teratogenic; therefore, women of child-bearing potential and men must agree to use adequate contraception (hormonal or barrier method of birth control) prior to study entry and for the duration of study participation. Should a woman become pregnant or suspect she is pregnant while participating in this study, she should inform her treating physician immediately.
- 3.1.7 Ability to understand and the willingness to sign an IRB-approved informed consent document

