6.2 Treatment Administration

Patients currently receiving or about to start treatment with an oral tyrosine kinase inhibitor for one of the major oncogenic drivers (EGFR, MET, BRAF, V600E, RET, HER2, Alk, or ROS-1) will be eligible. At the time of registration, blood samples will be obtained for plasma and other biomarker analyses (Appendix J), tobacco use (Appendix D) and performance status (Appendix K) will be determined. Treatment with an agent targeting the primary oncogenic driver will be continued until progression. If a new agent is approved for treatment of the primary driver, patients may be changed prior to progression at the investigator's discretion.

At the time of progression, patients will undergo repeat biopsy to determine PD-L1 staining and large scale genetic testing. Foundation Medicine testing is preferred but patients may have testing performed by other platforms including Guardant 360. Other platforms may be used after discussion with the principal investigator. Research plasma and tissue will be collected (Appendix J). Patients will also complete a detailed tobacco use questionnaire at the time of progression (Appendix E). Further, Performance Status will be determined (Appendix K). While awaiting results of testing, patients may continue the current treatment targeting the primary oncogenic driver.

Phase II Pilot Study Evaluating Strategies to Overcome Resistance at the Time of Progression
for Patients with Non-Small Cell Lung Cancers Harboring Major Oncogenic Drivers
Wake Forest Baptist Comprehensive Cancer Center (CCCFWU)
CCCFWU 62716
ClinicalTrials.gov: NCT02949843

If the PD-L1 testing result is $\geq 50\%$, patients will receive immunotherapy with either nivolumab or pembrolizumab as subsequent treatment. If patients have PD-L1 testing result that is $< 50\%$, the large scale testing will be used to determine the presence of absence of a secondary driver. For the purposes of the study, a secondary oncogenic driver will be considered an activating genetic change in a gene other than the primary oncogenic driver gene that has an effective treatment. These would include EGFR, Alk, ROS-1, MET, BRAF V600E, RET, and HER2. Classification of a genetic alteration as a secondary driver will be determined by the investigator.

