For patients without secondary oncogenic drivers, treatment will be categorized as subsequent line of treatment, targeting the primary oncogenic driver, or other treatment. For patients with secondary oncogenic drivers, treatment will be categorized as treatment targeting secondary oncogenic driver, subsequent line of treatment targeting the primary oncogenic driver or other treatment. Targeted treatments may include those treatments listed on NCCN Guidelines. Initial medication dose and dose modifications should be implemented according to standard of care guidelines.

Treatment will be administered on an inpatient or outpatient basis. Reported adverse events and potential risks are described in Section 9.0. No investigational or commercial agents or therapies other than those described below may be administered with the intent to treat the patient's malignancy.

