12.0 Statistical Considerations

12.1 Introduction

By design patients will be enrolled in this study prior to the determination of their PD-L1 status. In addition, among patients with low PD-L1 expression (<50%) it cannot be determined prospectively how many patients after disease progression will have a secondary oncogenic driver identified. Thus, patients upon enrollment may enter one of three arms to be determined at a later time – 1) PD-L1 expression $\geq 50\%$, 2) PD-L1 expression <50% with secondary oncogenic driver identified and 3) PD-L1 expression <50% without secondary oncogenic driver identified. It is anticipated that less than 50% of patients will have PD-L1 expression $\geq 50\%$, thus this arm – which is the focus of the primary objective – will take longer to fill. In order to manage the overall sample size expectations of this study, the design will allow enrollment to continue until 15 patients are enrolled in the PD-L1 expression $\geq 50\%$ arm (sample size needed based on Simon's two stage design described below). Each of the other two arms will allow enrollment until a minimum of 15 and maximum of 30 patients are enrolled into each arm. If the maximum (n=30) is reached in either of the PD-L1 expression < 50% arms, then new patients eligible for those arms will not be included in the follow-up assessments.

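### Overall survival is compared across three non-randomised biomarker cohorts with an unadjusted log-rank test only, although performance status and smoking are recorded at the OS time origin

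*Combined protocol and SAP*

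**What the plan says.** **Allocation.** Section 12.1 explains that "patients upon enrollment may enter one of three arms to be determined at a later time". The arms are PD-L1 at or above 50%, PD-L1 below 50% with a secondary driver, and PD-L1 below 50% without one. No randomisation is described.

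**Treatment.** Under Section 6.2, high PD-L1 "patients will receive immunotherapy with either nivolumab or pembrolizumab as subsequent treatment". Below 50%, treatment is mixed: for patients with a secondary driver, "treatment will be categorized as treatment targeting secondary oncogenic driver, subsequent line of treatment targeting the primary oncogenic driver or other treatment". Patients without a secondary driver also receive either primary-targeted or other treatment.

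**Aim.** Objective 2.2.1 reads "To compare the overall survival for patients receiving treatment targeting primary mutations, secondary mutations, or immunotherapy", and 5.2.1 ranks OS as the first secondary outcome.

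**Analysis.** The cohorts "will have OS estimated using Kaplan-Meier methods and survival rates will be compared using log-rank tests" (12.3). Section 12 names no stratum, covariate or regression model for OS. It calls the three-group response comparison exploratory but does not say so of OS.

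**Available data.** Entry allows "ECOG performance status of 0-3" (3.1.4). At progression, Section 6.2 adds "Further, Performance Status will be determined (Appendix K"; the form itself is Appendix L, and it also lists ECOG 4. Tobacco use at progression is on Appendix E. Sections 7.2 and 12.3 both start OS at progression. Section 12.3 tests smoking against mutation prevalence, and 5.2.4 sets tobacco use against PD-L1 group. ECOG has no stated analysis role.

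**The concern.** Nothing in this design balances prognosis across the cohorts. An unadjusted log-rank test cannot separate a cohort difference from a difference in case mix, and performance status is allowed to vary widely at entry and may worsen by progression. The plan measures it at exactly the date from which survival is counted and then leaves it out.

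Section 1.0 also ties smoking to the variable that defines the first arm: "High PD-L1 expression and response to immunotherapy has been reported in patients with oncogenic drivers who smoke cigarettes".

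What is at stake is the reading of the first secondary outcome. A small p-value, or separated curves, could be taken as evidence for one strategy over another when it reflects who was in each cohort.

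**Working it through.** **The plan's own figures.** No alpha, event count, power or hazard ratio is stated for OS, so there is no OS figure to reproduce. The primary design can be checked with P(reject) = Σ(x=1..8) P(X₁=x)·P(X₂ ≥ 4−x), X₁ ~ Bin(8,p), X₂ ~ Bin(7,p). This gives 0.0544 at p = 0.10 and 0.9046 at p = 0.40, against the stated 0.054 and 90.5%. That part is sound and is not affected here.

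**Inputs from the documents.** Arm sizes run from 15/15/15 to 15/30/30 (12.1, 12.6). The OS origin is progression. The test is an unstratified log-rank.

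**Inputs assumed.** Exponential survival with median 12 months in ECOG 0-1; hazard ratio 2 or 3 for ECOG 2-3; censoring uniform on 6-36 months; nominal alpha 0.05; no true arm effect. ECOG 2-3 shares per arm are varied.

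**Step 1: spurious hazard ratio at time zero.** With ECOG 2-3 shares a and b in two arms, it is [1+a(HR−1)] / [1+b(HR−1)].
- Shares 40% v 20%: HR 2 gives 1.4/1.2 = 1.17; HR 3 gives 1.8/1.4 = 1.29.
- Shares 50% v 15%: HR 2 gives 1.5/1.15 = 1.30; HR 3 gives 2.0/1.3 = 1.54.

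**Step 2: rejection rate of the three-group log-rank test.** Simulated with 3,000 or more trials per setting. Ranges cover both sets of arm sizes and both hazard ratios.

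| ECOG 2-3 share by arm | Unadjusted | Stratified by ECOG |
|---|---|---|
| Equal (30/30/30%) | about 5-6% | about 5-6% |
| 20/20/40% | 6.4-9.0% | 5.5-5.9% |
| 15/30/50% | 7.6-12.7% | 5.4-5.8% |

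The Monte Carlo standard error is √(0.055×0.945/3000) = 0.4 percentage points near 5.5%, and √(0.127×0.873/3000) = 0.6 near 12.7%. Repeat runs agree to within about one percentage point.

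**Step 3: sensitivity without censoring** (4,000 trials per setting, HR 2-3). Equal shares: 6.1-7.6% unadjusted, 6.3-7.0% stratified. Shares 10/30/60%: 13.0-22.8% unadjusted, 6.1-7.3% stratified. The pattern is the same: the excess appears only with systematic imbalance, and stratification returns the rate to its small-sample baseline.

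**Step 4: events available.** P(death) = 1 − [exp(−6λ) − exp(−36λ)]/(30λ), with λ = ln2/12 times the hazard ratio. This is 0.664 for ECOG 0-1, 0.860 at HR 2 and 0.932 at HR 3.
- Smallest case (15/15/15, 20/20/40%, HR 2): 33×0.664 + 12×0.860 = 32 deaths.
- Largest case (15/30/30, 15/30/50%, HR 3): 48.75×0.664 + 26.25×0.932 = 57 deaths.

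That carries one or two covariates, not more.

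**Step 5: pairwise power.** If every patient dies, two-sided alpha is 0.05 and the hazard ratio is 0.5, power is Φ(√(D·p(1−p))·ln2 − 1.96), where D is the number of deaths and p the share of patients in one arm. It is 47.5% for 15 v 15, 59.2% for 15 v 30 and 76.6% for 30 v 30. The OS comparison is not sized as a confirmatory test.

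**The case against.** The strongest reply has four parts.

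- **No documented imbalance.** Nothing in the documents links performance status to PD-L1 or to secondary drivers. The shares, the ECOG hazard ratio and the median are all assumed, and with equal expected shares the excess disappears. This stands, and it limits the claim to what can happen. A reader might infer that arms of 15-30 patients make chance imbalance inflate the test's error rate. They do not: the log-rank test already allows for chance imbalance, as the equal-share row shows.
- **Modest stakes.** This is a pilot, OS is secondary with no decision rule, and the stopping and success rules rest on response in the high PD-L1 arm. This also stands. But the plan still specifies a test for a stated comparative objective, and does not call it exploratory.
- **Smoking.** A reader might infer from Section 1.0 that smoking confounds OS. That text concerns PD-L1 expression and response to immunotherapy, not survival whatever the treatment. If smoking changes the response to immunotherapy, a main-effect covariate would not capture that. No size is calculated for smoking here, so it belongs in a sensitivity model only.
- **Adjustment cannot rescue the objective.** Biomarker status defines the cohorts, and treatment is mixed within both low PD-L1 arms. An adjusted hazard ratio would therefore not be the treatment comparison that 2.2.1 describes, and could look more causal than it is. This is correct, and is why the label must change along with the analysis.

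**Conclusion.** The gap is real, and closing it is a cheap improvement. The documents establish that the cohorts are not randomised, that the only OS comparison is an unadjusted log-rank test, and that ECOG and smoking at the time origin are collected but unused for OS. A systematic difference in performance status can therefore be read as an arm effect.

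Under the stated assumptions the unadjusted rejection rate is about 8-13% at shares of 15/30/50% and about 6-9% at 20/20/40%, against about 5-6% with ECOG strata. These are illustrations. The documents supply neither the imbalance nor the prognostic strength of ECOG in this population.

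A reader might go further and infer that such an imbalance will occur and will distort the result. The documents do not support that. The primary endpoint and its Simon design are untouched.

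**What to change.** In 12.3:

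1. Keep the Kaplan-Meier curves and the unadjusted log-rank test as descriptive.
2. Prespecify a log-rank test stratified by ECOG at progression, grouped as 0-1 against 2 or higher. Leaving the upper group open matters because Appendix L allows ECOG 4.
3. Prespecify a Cox model giving arm hazard ratios with confidence intervals, adjusted for ECOG at progression. Add ever/never smoking (Appendix E, question 1) as a second covariate in a sensitivity model only.
4. Tabulate ECOG and smoking at progression by arm.
5. Label the OS comparison exploratory, and a comparison of biomarker cohorts rather than of treatments.

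**Cost.** One paragraph and one table. Both variables are already on study forms that go to REDCap (Section 11.0), so no new data or visits are needed. The statistical price is one or two extra parameters on roughly 32-57 expected deaths under the assumptions above, and some loss of information from sparse strata. At a 15% share, a 15-patient arm has only 0.15×15 = 2.25 expected patients in the poorer ECOG group.

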5.2.2 Toxicities which will be measured using CTCAE version 4.0

5.2.3 Incidence of mutations in secondary genes

5.2.4 Rate of tobacco use and mutation burden by patient group based on PD-L1 expression (yes/no) at the time of progression.

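### Section 12.3 plans a secondary-gene mutation incidence for the two PD-L1 <50% arms but none for the PD-L1 ≥50% arm or overall, and Appendix J may not capture the data to supply it

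*Combined protocol and SAP*

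**What the plan says.** **Objective and outcomes.** Objective 2.2.2 is "To assess the incidence of secondary mutations in this population according to smoking status". Objective 2.2.1, directly above it, concerns patients progressing on a tyrosine kinase inhibitor and includes those who go on to immunotherapy. Outcome 5.2.3 is "Incidence of mutations in secondary genes", with no PD-L1 condition. Outcome 5.2.4 is "Rate of tobacco use and mutation burden by patient group based on PD-L1 expression (yes/no) at the time of progression".

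**Testing.** Section 6.2 has patients re-biopsied at progression for PD-L1 staining and broad sequencing together. The PD-L1 result then directs what follows. Looking for a secondary driver in the sequencing result is described only for PD-L1 below 50%.

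**Analysis.** Section 12.3 says "The incidence of mutations in secondary genes will be determined for patients in the two PD-L1 expression < 50% arms as well". It then relates smoking status (current, former, never) to the "prevalence of any mutations identified (present/absent" and adds: "These tests will be performed overall and then separately in the three arms defined above".

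**Definitions.** Section 1.0 speaks of "mutations in genes other than the primary driver gene (secondary mutations". Section 6.2 defines a secondary driver more narrowly, as an activating change in another gene that has an effective treatment. Section 12.3 does not say which of the two it counts.

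**Data form.** Appendix J asks for the PD-L1 score and directs the user to the secondary-driver section if it is below 50%. That section asks whether a secondary driver was found and which one. It has no field for other secondary-gene mutations.

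**The concern.** The objective asks about one population and the analysis section names a smaller one, without giving a reason. Followed literally, the plan would report a listed secondary outcome for PD-L1-low patients alone, even though sequencing is planned for PD-L1-high patients too.

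The plan itself treats PD-L1 as relevant. Outcome 5.2.4 compares mutation burden between PD-L1 groups, and section 1.0 notes: "High PD-L1 expression and response to immunotherapy has been reported in patients with oncogenic drivers who smoke cigarettes". So it cannot be taken for granted that incidence in the PD-L1-low arms stands for the whole population.

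The form raises a practical problem. If arm 1 patients skip the mutation section, arm 1 mutation status may not exist in analysable form. The arm 1 and overall smoking tests that 12.3 specifies, and the PD-L1 comparison in 5.2.4, would then have to be rebuilt from source reports.

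**Working it through.** **1. Which patients each place covers**

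| Place | Patients covered |
|---|---|
| Objective 2.2.2 | the study population, no PD-L1 limit |
| Outcome 5.2.3 | no PD-L1 limit |
| Outcome 5.2.4 | both PD-L1 groups |
| Section 6.2, sequencing | patients at progression, PD-L1 not yet known |
| Section 12.3, incidence | the two PD-L1 <50% arms |
| Section 12.3, smoking tests | overall and each of three arms |
| Appendix J, mutation section | PD-L1 <50% |

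The incidence sentence and the form stand apart from the rest.

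**2. Share left out.** Inputs: arm 1 has 15 patients and the other two arms 15 to 30 each (12.1); the total is 45 to 75 (12.6).

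- Minimum: 15/45 = 33%.
- Maximum: 15/75 = 20%.

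These shares hold only if incidence is counted within the capped arms. Section 12.1 drops over-cap patients from the follow-up assessments, while the schedule in 6.1 places the biopsy after first progression. Their sequencing results may therefore be kept. The share left out is then the PD-L1-high share among those sequenced, which 12.1 gives only as less than 50%.

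**3. Effect on the estimate.** Let w be the share left out, and I_low and I_high the incidence in the two PD-L1 groups.

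All-patient incidence = (1 − w) × I_low + w × I_high

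Error of the restricted figure = w × (I_low − I_high)

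The documents give neither rate. Assume I_low = 20% and I_high from 10% to 40%:

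- 45 patients, I_high 10%: (2/3)(20) + (1/3)(10) = 16.7%.
- 45 patients, I_high 40%: (2/3)(20) + (1/3)(40) = 26.7%.
- 75 patients, I_high 10%: 0.8(20) + 0.2(10) = 18%.
- 75 patients, I_high 40%: 0.8(20) + 0.2(40) = 24%.

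In this range the restricted 20% is off by at most 6.7 points, and by nothing if the rates are equal. In general, each 10-point difference between PD-L1 groups moves the figure by 3.3 points at 45 patients and 2 points at 75.

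**4. Precision.** The plan's own figures reproduce: the largest exact (Clopper-Pearson) 95% half-width is 26.1% at n = 15 and 18.7% at n = 30, as in 12.4. With the same method, adding arm 1 lowers it from 18.7% to 15.3% at minimum size (30 to 45 patients) and from 13.2% to 11.8% at maximum size (60 to 75). The gain is modest.

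**5. Definition and the within-arm tests.** For an arm of N patients with m1 positive and m0 negative, the variance of the positive count among the n_s patients in a smoking category is n_s(N − n_s)·m1·m0 / [N²(N − 1)].

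- If positive means a secondary driver, m0 = 0 in arm 2 and m1 = 0 in arm 3, because those arms are defined by driver status. The variance is zero and neither test is informative.
- If positive means any mutation in a gene other than the primary driver, arm 3 can vary. Arm 2 cannot: every patient there has a secondary driver and so is positive under either definition.

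The broader meaning fits 12.3 better, but it rescues the arm 3 test only.

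**The case against.** **The sentence does not say that arm 1 is excluded.** Its closing words could mean in addition to the high PD-L1 arm. That is possible, but the sentence follows one on response rates in the same two arms, and no arm 1 incidence appears anywhere. It is probably loose drafting rather than a deliberate restriction, and a sentence would settle it.

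**Objective 2.2.2 is partly served already.** It asks for incidence by smoking status, and the overall smoking test needs the full smoking-by-mutation table, from which proportions can be read. This stands and reduces the point. What remains missing is a stated estimate with an interval, and a form that supplies the arm 1 data.

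**If secondary drivers are meant, the restriction has a rationale.** Section 6.2 and Appendix J classify drivers only when PD-L1 is below 50%. That explains the wording, but it conflicts with the smoking tests in arm 1 and overall.

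**Stronger readings that the documents do not support.** A reader might infer from the reported link between smoking and high PD-L1 that smokers are removed from the smoking analysis. They are not: those tests include arm 1, and the documents give no smoking rates. A reader might also infer that the 30-patient caps distort the incidence. Section 12.1 removes over-cap patients only from follow-up assessments, which does not clearly touch the mutation result obtained at progression.

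**Conclusion.** The point holds as a minor inconsistency. The incidence analysis in 12.3 names a narrower set of patients than objective 2.2.2 and outcome 5.2.3, and the routing in Appendix J may leave arm 1 mutation status uncaptured for analyses that the plan itself specifies.

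The stated estimate omits 33% to 20% of patients at the planned arm sizes, or an unknown share below 50% if over-cap patients count. The direction and size of any bias are unknown. The 6.7-point figure rests on assumed rates, and the bias is zero if incidence does not vary with PD-L1.

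It would be wrong to conclude that arm 1 goes unsequenced or that objective 2.2.2 goes unanswered: sequencing is planned and the overall smoking test addresses part of the objective. The Simon two-stage test, treatment assignment and safety are unaffected.

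**What to change.** 1. **Section 12.3, population.** Estimate incidence with an exact 95% confidence interval, overall and by smoking status, among all patients with a sequencing result at progression. Keep the PD-L1 <50% figure as a subgroup.
2. **Section 12.3, definition.** State that the outcome counts any mutation in a gene other than the primary driver gene, as in section 1.0. Report the secondary-driver rate separately if it is wanted. Acknowledge that a present/absent test in arm 2 is uninformative under either definition.
3. **Appendix J.** Record any secondary-gene mutation (yes/no and identity) for every patient, whatever the PD-L1 result.

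The cost is a few sentences in 12.3 and a small form change. Sequencing is already planned, so no new procedure is needed. The downside is one more form section to complete for PD-L1 ≥50% patients. The form change is best made early, since results not recorded prospectively would have to be retrieved from source reports.
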